To compare the incidence of mechanical ventilation or death in subjects with severe COVID-19 given placebo or oral duvelisib.	The primary end-point is a composite endpoint of mechanical ventilation or death within 4 weeks of randomization.
Secondary	
Secondary Objectives are to compare the duvelisib cohort to the placebo cohort with respect to:
 
1) Days to recovery as assessed by ACTT endpoints as the time to recovery (Day 1 through Day 29) to satisfy a score of ≥ 5 from the following eight categories from the NIAID ordinal scale. The scale is as follows: 1. Death; 2. Hospitalized, on invasive mechanical ventilation or extracorporeal membrane oxygenation (ECMO); 3. Hospitalized, on non-invasive ventilation or high flow oxygen devices; 4. Hospitalized, requiring supplemental oxygen; 5. Hospitalized, not requiring supplemental oxygen - requiring ongoing medical care (COVID-19 related or otherwise); 6. Hospitalized, not requiring supplemental oxygen - no longer requires ongoing medical care; 7. Not hospitalized, limitation on activities and/or requiring home oxygen; 8. Not hospitalized, no limitations on activities.2) Duration of hospitalization3) Death within 29 days of randomization4) ICU transfer within 29 days of randomization5) ECOG performance status at day 15 and 29 of randomization6) Incidence of grade III-V adverse events or SAEs (as defined by CTCAE version 5)7) Documented secondary bacterial or viral infection within 29 days of randomization.8) Mean frequencies of Th1 and Th17 T cells in blood mononuclear cells at 1, 2 and 4 weeks9) Mean levels of inflammatory serum biomarkers at 1, 2 and 4 weeks10) Gene expression profiles of T cells at 1, 2 and 4 weeks

OBJECTIVES	ENDPOINTS
11) Median titers of IgG antibodies to SARS-CoV-2 at 4 weeks 12) Survival at day 50-60 after randomization	

3. Background

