3.1 Study Rationale

COVID-19 patients have a poor prognosis, especially in the setting of co-morbidities, the presence of inflammatory serum markers, and declining oxygenation levels, with reported frequency of ICU transfer up to 50% and death of 25% (1, 2). Serum inflammatory markers in patients with severe COVID-19 including those that require ICU care and respiratory support with mechanical ventilation are reported to be higher than in patients with less severe disease (1), and COVID-19 patients develop a pattern of interstitial pulmonary infiltrates (3, 4) that are similar to those seen among patients that develop auto-immune pneumonitis in the setting of treatment with monoclonal antibodies that block immune check-point signaling (5). Taken together, these clinical and laboratory observations have led to the hypothesis that COVID-19 leads to hyper-immune activation, also termed “cytokine storm”(6). Immunomodulatory clinical interventions that are currently being evaluated included antibodies that block IL6 signaling (22 trials), IL1 signaling (5 trials), and tyrosine kinase inhibitors to Bruton’s tyrosine kinase (BTK) (7), Janus2 Kinase (JAK) (2 trials). The common theme in these studies is the hypothesis that intra-cellular signaling pathways of immune cells are hyper-activated, that immune hyperactivation contributes to alveolar damage and impairments in gas exchange, and that clinical interventions to block intra-cellular tyrosine kinase-mediated signaling pathways activated during COVID-19 will prevent or reverse the alveolar damage and hypoxemia that characterizes this disease. Recently, clinical data from CLL patients treated with duvelisib, a dual PI3K gamma/delta inhibitor, indicate lower levels of serum inflammatory markers during PI3Ki exposure (8). Addition of PI3K inhibitors, including duvelisib, during *ex vivo* expansion of T cells stimulated with anti CD3/CD28 beads indicates PI3K-inhibition appears to block differentiation of T cells from naïve/central memory to effector phenotypes, increases frequencies of CD8+ T cells, and improves *in vivo* persistence and anti-tumor activity when PI3Ki-expanded T cells are reinfused *in vivo* (9). Paradoxically, continuous exposure to duvelisib over a period of months has been associated with both opportunistic infections (10, 11) as well as auto-immune toxicities (12, 13), supporting the idea that duvelisib is an immunomodulatory drug, and indicating that short-term exposure to PI3Ki may have different immunological consequences than long-term exposure.

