3.3 Inflammation as part of lung pathology in COVID-19

Following initial infection of the nasal pharyngeal epithelium, SARS-CoV-2 infection can spread to the lungs where it causes viral pneumonia, producing symptoms of dyspnea secondary to hypoxemia (2, 14), with radiographs showing interstitial infiltrates in the lung periphery (3, 4), collectively creating a novel disease entity termed COVID-19. Severe pneumonia can progress to Adult Respiratory Distress Syndrome (ARDS) requiring intubation and mechanical ventilation (1, 2). The development of severe pneumonia and respiratory failure leading to ARDS has been associated with elevated levels of serum cytokines (1, 6), suggesting that SARS-CoV-2 pulmonary infection in these patients has led to a “cytokine storm”, and that administration of drugs that inhibit cytokine release or block cytokine signaling may be of clinical benefit in patients with COVID-19. A recent report from Wuhan described 548 hospitalized patients with COVID-19, half of whom had severe disease (defined by the 2019 American Thoracic Society Guidelines (16)) of which one third required mechanical ventilation and one third died (1). Age, male gender, elevated leukocyte counts, LDH, troponin and glucose levels were associated with an increased risk of death among COVID-19 patients with severe disease in a multi-variable model, and treatment with steroids, a non-specific immunosuppressive, were associated with an increased risk of death. Serum cytokine levels for IL-2R, IL-6, IL-10, and TNF- α were significantly higher in COVID-19 patients with severe disease than nonsevere patients (1). These data and other reports of similar findings indicate that 1) patients with severe disease at a higher risk of death can be identified by simple clinical and laboratory assessments, 2) that disease severity is associated with a heightened inflammatory state, and 3) interventional studies to reduce inflammation in patients with high-risk disease could be of benefit to patients. A separate analysis of Wuhan patients with severe COVID-19 indicated that patients with severe disease had decreased numbers of total T cells, CD8+T cells and CD4+T cells, and that lower T cell numbers were negatively correlated with patient survival (17). Of note, lower T cell numbers in patients were also associated with higher IL-6, IL-10 and TNF- α cytokine levels, and COVID-19 patients treated in the ICU had higher levels of expression of the co-inhibitory markers PD-1, LAG-3 and TIM-3 (17), suggesting that inflammation may cause quantitative and qualitative suppression of T cell function.

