Evaluable subjects will be all subjects who were randomized to receive duvelisib or placebo. The definition of secondary endpoints are listed in section 2. The descriptive statistics will mainly be applied to all secondary endpoints by treatment arms separately, such as frequency and percentage for categorical endpoints and mean, median, and standard deviation for numerical endpoints. They will be compared between treatment arms by Fisher's Exact test for categorical endpoints and Wilcoxon Rank-Sum test for numerical endpoints. For biomarkers measured repeated over time, generalized estimating equation (GEE) model will be used to test the difference in change pattern over time by two treatment groups using a nonlinear model. P-value will be adjusted for multiple comparison if necessary. Time to recovery is as the days from randomization to reach the desired NIAID ordinal scale ≥ 5 , a log-rank test will be used to compare the difference between the two arms. Survival rate at day 50 - 60 will be estimated by Kaplan-Meier method with log-rank test.

Interim Analysis for futility

The responsibility of any data-informed recommendations regarding continuing/stopping the study or modifying the study design/protocol be restricted to the independent data monitoring committee (IDMC), which is a part of the Winship data safety monitoring committee (DSMC). Upon 20 enrolled for each arm, an interim analysis will be carried out by two-sided Mantel-Haenszel test. O'Brien-Fleming boundary for futility is 2.373 on the Z score (equivalently: 0.991 on the fixed sample p-value scale). The trial may be terminated due to futility, or

Protocol Title: Duvelisib Ameliorates Manifestations of Pneumonia in Established Novel Coronavirus Infection (DAMPEN-CI)

following review by the IDMC of clinical and laboratory immune-monitoring data. Otherwise, the trial will continue enrolling patients until all 80 patients enrolled.

Stopping Rule for Safety

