At the interim analysis (20 patients/arm), the incidence of death or mechanical ventilation, grade ≥ 3 elevations in liver transaminases, or neutropenia will be estimated. We assume that the underline rate is 40%, 10%, or 24% for the three incidences in placebo group respectively, and if the rate in duvelisib group is $\geq 15\%$ higher than that in the placebo group in either of the three incidences, the trial may be stopped due to the safety concern. It also translates to stop the study if 3 or more excess events in duvelisib group are observed in either of the three incidences. Operating Characteristics, the probability of trial stopping due to ≥ 3 excess events based one simulation study, is listed in the below table.

AEs	Underline event rate in Placebo arm	Underline event rate in Duvelisib arm						
		5%	10%	20%	30%	40%	50%	60%
death or mechanical ventilation	40%	0%	0.02%	0.7%	4.8%	16.6%	37.4%	62.7%
grade ≥ 3 elevations in liver transaminases	10%	0.79%	5.7%	32.8%	65.8%	87.9%	97.2%	99.7%
neutropenia	24%	0.07%	0.6%	7.3%	26.1%	52.7%	77.3%	92.6%

In addition to the study stopping rules based an interim analysis, the Independent Data Monitoring Committee (IDMC) will review, on a monthly basis, the number of Grade 3 and/or Grade 4 adverse events in each arm, including neutropenia and elevated transaminases, and consider stopping or suspending accrual to the study if the frequencies of Grade 3 or Grade 4 adverse events are significantly higher among subjects in the duvelisib arm compared with subjects in the control arm.

Analysis of Safety Data

The primary safety endpoints include death or mechanical ventilation, grade ≥ 3 elvation in liver transminases, and neutropenia within 4 weeks. The cumulative incidence rate of each safety endpoint will be calculated with 95% confidence interval by randomized arms, and compared by Fisher's exact test.

Handing of Missing Data

For the safety endpoints and secondary endpoints, missing data will not be imputed, summaries and analyses will be based on the observed cases. For the primary efficacy analysis, every effort will be made from the informed consent form design to clinical follow up to reduce the missing data. Patients withdraw consent before the primary endpoint can be measured will be replaced.

Demographics and Baseline Characteristics

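### Length of hospital stay goes to a plain Wilcoxon test with no rule for in-hospital deaths or for patients still admitted at day 29

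*Combined protocol and SAP*

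**What the plan says.** Section 15.1, Analysis of Secondary Endpoints, refers the reader elsewhere for definitions: "The definition of secondary endpoints are listed in section 2". Section 2 gives only the words "Duration of hospitalization", with no start, end, cap or treatment of death.

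Section 15.1 also fixes three things that apply to this endpoint:

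- **Analysis set.** "Evaluable subjects will be all subjects who were randomized to receive duvelisib or placebo", so patients who die are included.
- **Test.** Fisher's exact test for categorical endpoints and the "Wilcoxon Rank-Sum test for numerical endpoints".
- **Missing data.** For secondary endpoints, "missing data will not be imputed, summaries and analyses will be based on the observed cases".

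Time to recovery is treated differently: "a log-rank test will be used to compare the difference between the two arms". Survival at day 50-60 gets Kaplan-Meier and a log-rank test. Hospital stay has no such provision and falls under the default rule.

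**The concern.** A rank test on length of stay reads a shorter stay as better. That is sound only if every stay ends in live discharge. A death cuts the stay short, so the number alone cannot tell a death on day 6 from a discharge on day 6.

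The plan leaves two readings open:

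- **The stay ends at death.** Deaths before the typical discharge day take favourable ranks. A drug that prevents them can appear to prolong stay, and one that causes them can appear to shorten it.
- **Deaths are dropped as having no discharge.** The arms are then compared among survivors only, a group formed after randomization. If rescued patients are sicker and stay longer, the arm that saved them looks worse.

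Patients still in hospital at day 29 raise a smaller question: their stay is incomplete, and no rule says what value they take. With nothing written down, either choice could be made after the data are seen.

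**Working it through.** **1. The plan's own figure.** The documents give no figure for this endpoint. The only related one is power above 80% for the primary composite (Section 15.1, Power Calculation): 40 per arm, 40% vs 15%, two-sided 10%. Pooled rate 0.275; null SE = √(2 × 0.275 × 0.725 / 40) = 0.0998; alternative SE = √((0.40 × 0.60 + 0.15 × 0.85) / 40) = 0.0959; z = (0.25 − 1.645 × 0.0998) / 0.0959 = 0.89, so power is 81.5%. It reproduces. I use the same sample size and level below. The plan states no level for secondary tests, so 10% is an assumption here.

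**2. Inputs.** Mortality in the documents: 25% (Section 3.1); among severe inpatients, "one third required mechanical ventilation and one third died" (Section 3.3); and locally 22% intubated × 37% of those dying = 8.1% of admitted patients (Section 15.1). Assumed, because the documents are silent: duvelisib-arm mortality, time to death, survivors' stay, and lognormal spread (log-SD 0.6 for survivors, 0.5 for deaths).

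**3. Direction when the stay ends at death.** Let p_c and p_d be control and duvelisib mortality, and q the chance that a survivor's stay exceeds a time to death. Suppose stays and death times are distributed alike in both arms. The chance θ that a duvelisib stay is longer than a placebo stay (ties split) is then

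θ = ½ + (p_c − p_d)(q − ½), with q = Φ(ln(survivor median / death median) / √(0.6² + 0.5²)).

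θ above ½ goes against duvelisib. The sign depends only on whether deaths come before or after the typical discharge.

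**4. Direction when deaths rank worst.** Deaths then always exceed survivors' stays (q = 0), so θ = ½ − ½(p_c − p_d). This is below ½ whenever duvelisib lowers mortality.

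**5. Results.** Percentages are the simulated share of trials with p < 0.10, against / for duvelisib. Stays are alike among all survivors.

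| Mortality, placebo vs duvelisib | Median days, deaths / survivors | q | θ, raw stay | Raw stay, against / for | θ, deaths worst | Deaths worst, against / for |
|---|---|---|---|---|---|---|
| 30% vs 10% | 6 / 12 | 0.81 | 0.563 | 26% / 0.4% | 0.400 | 0.1% / 44% |
| 25% vs 10% | 10 / 10 | 0.50 | 0.500 | 5% / 5% | 0.425 | 0.2% / 31% |
| 25% vs 10% | 14 / 8 | 0.24 | 0.461 | 1% / 15% | 0.425 | 0.3% / 32% |
| 8% vs 3% | 6 / 12 | 0.81 | 0.516 | 7% / 3% | 0.475 | 2% / 11% |

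Repeat runs of the first row gave 24% to 26% against. Repeat runs of the last row gave 7% to 9% against and about 3% for. In the first row mean stay is about 1.5 days longer on duvelisib, while days alive and out of hospital to day 29 favour it by about 3 days. With the first row's mortality reversed (30% on duvelisib, 10% on placebo), the harmful arm shows a significantly shorter stay in about 24% of trials.

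**6. Deaths dropped.** At 25% vs 10%, the result is about 5% each way if rescued patients stay as long as other survivors. If rescued patients stay a median of 20 days, it is 16-21% against and about 1% for. Ranking deaths worst remained in the right direction across all the 25% vs 10% scenarios, including those with long rescued stays: 0.2-1.5% against, 13-32% for.

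**7. Control.** With 25% mortality in both arms, all three methods give about 5% each way. The distortion arises only when mortality differs.

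**The case against.** A reader might infer that the plan counts deaths as short stays, or that the comparison generally runs opposite to benefit. The documents support neither. They are silent on death, and under an observed-case rule a patient without a discharge date could equally be left out. Death is not necessarily an early event either. Section 9.2 excludes ventilated patients at randomization, so a median time to death of 6 days is not obviously typical. With late deaths and short survivor stays, the raw comparison leans the right way.

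The mortality contrast is also assumed. The plan aims to cut a composite of ventilation or death from 40% to 15%, counts high-flow oxygen and Bi-PAP as ventilation, and does not say how much of the reduction is death. At the local figure of about 8% the distortion is small.

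Finally, this is one of 12 secondary endpoints, mainly summarized descriptively, and no decision rule uses it. Death is in the primary composite, is tested separately at 29 days, and is followed to day 50-60. A careful reader would see mortality next to length of stay.

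All of this stands, and it limits the size and the consequence. It does not supply the missing rule: neither open reading ranks an in-hospital death below a live discharge. A result whose direction depends on when deaths happen is hard to interpret whichever way it falls.

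**Conclusion.** The point holds as a gap in the analysis rule. Hospital stay is undefined for in-hospital death and for patients still admitted at day 29, and the default test does not count death as a bad outcome under either available reading.

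The size cannot be fixed from the documents. When duvelisib lowers mortality, the chance of a significant result against it on raw stay runs from about 1% to about 26% in the tabulated scenarios, where 5% would be neutral. The high end needs frequent, early deaths. The effect vanishes when death and discharge times are alike, and it reverses when deaths are late. These figures rest on assumed stay lengths, death times and mortality differences, and on borrowing the primary analysis's 10% level.

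The matter should be settled before unblinding. It does not affect the primary analysis.

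**What to change.** Add a few sentences to Section 15.1, with a matching definition in Section 2:

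- **Preferred endpoint.** Hospital-free days from randomization to Day 29. Patients who die by Day 29 score 0, and so do patients still in hospital at Day 29. Compare the arms by the Wilcoxon test already planned, and state how days of readmission are counted.
- **Alternative.** Keep length of stay but give deaths the worst rank in the same test, with patients alive and still in hospital at Day 29 ranked between live discharges and deaths.
- **Description only.** Report raw length of stay in survivors by arm, without a test.

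The cost is SAP wording. Section 8.1 already follows patients for discharge and death, so no new data or patients are needed. The trade-off is that the endpoint becomes a composite of stay and death and partly overlaps the separate mortality endpoint. A favourable result should therefore be read alongside mortality, not as independent evidence of faster discharge.

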opportunity to stop the trial early due to futility or safety concerns. The only groups that will have access to unblinded interim data: (a) an independent data monitoring committee (IDMC); and (b) an independent statistical team whose role will be to generate the reports to be reviewed by the IDMC. The responsibility of any data-informed recommendations regarding continuing/stopping the study or modifying the study design/protocol be restricted to the IDMC.

Power Calculation

The reported incidence of death or mechanical intubation for patients with severe COVID-19 is approximately 40% (1). Local experience with COVID-19 patients at the Emory hospitals is consistent with this estimate, as 29% of all SARS-CoV-2 positive patients (n=800) are admitted to the ICU with COVID-19, and that 22% of all admitted patients are intubated, and 37% of intubated patients die in hospital. A favorable and clinically significant result from treatment with duvelisib in high-risk COVID-19 patients would be to reduce the composite incidence of death/mechanical ventilation from 40% to 15%. A sample size of 40 subjects for each treatment group will have >80% power to detect a 25% absolute reduction in the proportion of subjects who experience death or mechanical ventilation, comparing a predicted proportion of 40% death or intubation in the control arm to 15% death or intubation in the experimental arm receiving duvelisib treatment. The calculation is based on 10% type 1 error rate and two-sided Mantel-Haenszel test with one planned interim analysis when approximately 50% of sample enrolled (N=20/treatment). For

Analysis of Primary Endpoints

Analysis of the primary end-point will be based upon an intent-to-treat analysis of all subjects who are randomized to receive duvelisib/placebo. The primary endpoint is the proportion of patients who will require mechanical ventilation or experiencing death within 4-weeks (29 days) after randomization, which will be estimated with the corresponding 95% Clopper-Pearson confidence interval for the two arms separately. Fisher's Exact test will be used to test the difference between the two arms. In addition, a logistic regression will be used to estimate the odd ratio between the two arms controlling for the baseline covariates for an improved precision of the estimation (30).

Analysis of Secondary Endpoints

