9. Dilute cell/CryoStor mixture immediately with appropriate culture medium. This can be performed in a single step. The dilution medium should be between 20–37 °C. A dilution ratio of 1:10 (sample: medium) or greater is recommended.

10. Plate cells appropriately.

11. Culture the cells or use immediately.

Shipment:

Patient samples from secondary sites will be shipped in real-time overnight on Monday-Wednesday so that samples will be received no later than Friday. Each sample will be shipped on adequate amounts of dry ice. Emory University will cover the cost for shipment of the patient samples

APPENDIX H: Table to guide the IDMC during review of potential toxicity in the duvelisib arm at the time of the interim safety analysis

Table 1: Approximate probability of observing excess instances of mechanical ventilation or death in the duvelisib treatment arm at the time of the interim analysis.

		True Underlying Duvelisib Rate								
		20%	25%	30%	35%	40%	45%	50%	55%	60%
Approximate probability of observing $\geq X$ excess instances of mechanical ventilation or death in the duvelisib arm compared to placebo	X = 0	7.9%	15.2%	25.2%	37.2%	50.0%	62.6%	73.9%	83.2%	90.2%
	X = 1	3.9%	8.6%	15.9%	25.7%	37.3%	50.0%	62.5%	73.9%	83.4%
	X = 2	1.7%	4.4%	9.1%	16.3%	25.9%	37.4%	50.0%	62.6%	74.1%
	X = 3	0.7%	2.0%	4.8%	9.5%	16.6%	26.1%	37.5%	50.0%	62.7%
	X = 4	0.2%	0.8%	2.3%	5.1%	9.8%	16.8%	26.1%	37.4%	50.0%

Note: The true underlying placebo rate is assumed to be 40% in this table

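### The interim futility boundary (Z = 2.373, p = 0.991) is the O'Brien-Fleming rejection value and leaves the plan without a working numerical futility criterion

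*Combined protocol and SAP*

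**What the plan says.** Section 15.1 (Study design) plans one interim analysis at half enrolment, described as an "opportunity to stop the trial early due to futility or safety concerns". The Power Calculation paragraph sets the error rate: "The calculation is based on 10% type 1 error rate and two-sided Mantel-Haenszel test with one planned interim analysis". It also states that "A sample size of 40 subjects for each treatment group will have >80% power to detect a 25% absolute reduction", from 40% to 15%.

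Under Interim Analysis for futility, the plan says "Upon 20 enrolled for each arm, an interim analysis will be carried out by two-sided Mantel-Haenszel test". It then gives the O'Brien-Fleming "boundary for futility is 2.373 on the Z score (equivalently: 0.991 on the fixed sample p-value scale"). The action is discretionary: "The trial may be terminated due to futility", or after the IDMC has reviewed clinical and immune-monitoring data. The text does not say which arm a positive Z favours, or whether the trial stops above or below the boundary.

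At the same look, the Stopping Rule for Safety covers three endpoints, including death or mechanical ventilation. It translates into a rule to "stop the study if 3 or more excess events in duvelisib group are observed". Appendix H, Table 1 gives the IDMC the "Approximate probability of observing excess instances of mechanical ventilation or death in the duvelisib treatment arm at the time of the interim analysis", as an aid to judging toxicity. Sections 8.2 and 16.3 mention futility without a threshold.

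**The concern.** A futility boundary should identify interim results from which a final success is unlikely. At half the information, such boundaries normally lie near Z = 0 in the direction of benefit. For scale, an O'Brien-Fleming-shaped futility-only bound with one-sided alpha 0.05 lies between about Z = 0.0 and Z = 0.5, for assumed type II errors of 0.05 to 0.20. A value of 2.373 looks instead like a boundary for rejecting the null hypothesis, and p = 0.991 puts it in the tail where duvelisib does worse.

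If so, the committee has a printed number that cannot do the job the section assigns to it. With equal event counts in the two arms, or one or two more events on duvelisib, the number points to continuing. Up to 40 more severely ill participants could then be randomized with little prospect of a positive result.

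**Working it through.** **Inputs.** Two-sided alpha 0.10, two looks, interim at 20 per arm, 40 per arm in total, event rates of 40% and 15%, and the safety rule of 3 or more excess events (all section 15.1). Allocation is 1:1 (section 1.2).

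**1. Reproducing the printed boundary.** For two equally spaced looks, classical O'Brien-Fleming limits are c√2 at the first look and c at the second. The constant c is chosen so that the total two-sided rejection probability is 0.10 when corr(Z₁, Z₂) = √0.5.
- c = 1.678, so the first-look limit is 1.678 × 1.4142 = 2.373.
- Φ(2.373) = 0.991. The two-sided p for 2.373 is 2 × (1 − 0.9912) = 0.018.
- The final-look limit of 1.678 has two-sided p = 0.0934.

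Both printed figures are reproduced to three digits, as a **rejection** boundary. The Lan-DeMets O'Brien-Fleming variants give 2.33 and 2.54, so the match is to the classical form. The stated power also reproduces: 81.5% by the fixed-design normal approximation.

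**2. Three possible readings.** All 21 × 21 interim tables at 20 per arm were enumerated, using the Mantel-Haenszel Z with hypergeometric variance and no continuity correction.

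*(a) Harm side, the reading that fits p = 0.991.* The boundary needs at least 6 excess duvelisib events (6 vs 0). With 8/20 on placebo it needs 16 on duvelisib: 15 vs 8 gives |Z| = 2.21 and 16 vs 8 gives 2.55. Stopping probabilities are:

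| True rates, placebo/duvelisib | Boundary | Safety rule, plan's table | Safety rule, exact | Either rule, exact |
|---|---|---|---|---|
| 40/40 | 0.8% | 16.6% | 21.0% | 21.0% |
| 40/50 | 3.8% | 37.4% | 43.9% | 43.9% |
| 40/60 | 12.9% | 62.7% | 68.9% | 68.9% |

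No table crosses the boundary with fewer than 3 excess events, so it adds 0.0 points. The plan's safety figures agree with a normal approximation without continuity correction, hence the gap to the exact values.

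*(b) Stop unless duvelisib is better by 2.373.* This would stop 75% of trials at the design effect of 40% vs 15%, which is incompatible with more than 80% power.

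*(c) Stop if |Z| ≥ 2.373.* This is the ordinary two-sided rejection rule. Its benefit side is an efficacy stop, which is not among the purposes section 15.1 gives for this look.

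**3. Size of the gap on reading (a).** Appendix H at 40/40 gives 50.0% for X = 0 and 16.6% for X = 3. So 50.0 − 16.6 = 33.4% of no-effect trials have 0 to 2 excess duvelisib events and meet neither criterion on this endpoint (exact: 35.4%).

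The chance of a final result favouring duvelisib, testing at two-sided 0.10, is then:
- After 0 to 2 excess events, with no true effect: 0.4% (Mantel-Haenszel) or 0.2% (Fisher).
- After an 8 vs 8 tie, with the full 40/15 effect in the second half: 21% (Mantel-Haenszel) or 13% (Fisher). By Mantel-Haenszel, ties at 5 vs 5 and 3 vs 3 give 29% and 36%.

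**4. An example bound.** Stop if duvelisib events equal or exceed placebo events (Z for benefit ≤ 0). Stopping probability: 56% at 40/40, 4.9% at 40/15, 11% at 40/20, 20% at 40/25. Exact power at 40/15 if the bound is always followed falls from 82.2% to 81.1% (Mantel-Haenszel) or from 75.5% to 74.8% (Fisher).

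**The case against.** The arithmetic is not in dispute. The strongest objections are these.

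- **The plan does print a number, and its direction is inferred.** This is true. The defect visible on the page is a missing sign and direction, and redundancy with the safety rule holds only on the harm-side reading. The other two readings do not give a usable futility rule either, so the defect remains.
- **Text may be missing.** The Power Calculation paragraph breaks off at the word For, where boundary details might have stood. Nothing is claimed about that text. The futility sentence itself is complete, and sections 8.2 and 16.3 and Appendix H supply no other threshold.
- **An efficacy stop may have been meant.** Section 8.2 lists demonstrated efficacy and a met primary endpoint among the reasons for termination. This keeps relabelling open. The heading of the interim paragraph, the purpose given in section 15.1 and section 16.3 all point to futility.
- **The consequences are limited.** Stopping is discretionary, the IDMC sees unblinded data and reviews grade 3 and 4 events monthly, and the type I error of the final test is unharmed. All of this stands, but none of it is a criterion for lack of benefit.
- **Some illustrations can be read as selective.** The 0.4% is low by construction because it assumes no effect, and the 21% belongs to one particular tie, hence the range shown above. At five enrolments a month and a 29-day endpoint, about 5 of the remaining 40 would be enrolled before the interim outcomes were complete unless accrual pauses. The realistic saving is then nearer 35.

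**Conclusion.** The concern holds. The printed futility boundary is the two-look O'Brien-Fleming rejection value for two-sided alpha 0.10, and no reading examined makes it a working futility rule. On the reading that fits p = 0.991, it adds 0.0 points to the safety rule's stopping probability, and about a third of no-effect trials (33.4% from Appendix H, 35.4% exact) meet no printed criterion on this endpoint.

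The identification of the boundary rests only on the plan's own alpha, number of looks and interim timing. The redundancy result assumes the harm-side reading, 20 evaluable participants per arm and no continuity correction. The probabilities also assume a 40% placebo rate. Type I error is not inflated. What is lost is the futility function of the only interim look, and this is an incorrect decision threshold that should be corrected before that look takes place.

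**What to change.** The sponsor should first state what the boundary was meant to do and reconcile sections 8.2, 15.1 and 16.3.

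**If futility was intended**, replace the sentence giving 2.373 and 0.991 with a non-binding bound in the direction of benefit. State the sign of Z, the side on which stopping is recommended, and the stopping probabilities under no effect, the design effect and smaller effects. Apply it to 20 per arm with known day-29 status, and state that the final test keeps the full two-sided 0.10.

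The example above (recommend stopping when duvelisib events equal or exceed placebo events) is one of several possible bounds. It includes every outcome with 3 or more excess events on the composite, so the text should explain how it and the safety rule fit together on that endpoint.

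**If an efficacy stop was intended**, label 2.373 as the efficacy boundary, use 1.678 (two-sided p = 0.0934) at the final analysis, and still give a separate futility bound if the trial is to be stoppable for futility.

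**Cost.** Protocol and SAP wording only. If the example bound is followed, power at 40/15 falls by about 1 point, and the risk of stopping a trial with a smaller true benefit is 11% at 40/20 and 20% at 40/25.
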